There is evidence in the literature for altered nociception in patients with FM⁹. FM is also characterized by heightened pain sensitivity to sensory stimuli, possibly as a result of the changes in the central processing in the brain, referred to as central sensitization¹. From a mechanistic perspective, the abnormal efferent activity could be reflected in the affected skeletal muscle. Our study objective is to explore this possibility using image texture feature analysis in B-mode US imaging. We believe that this may be possible since we have previously shown that texture features can not only discriminate between healthy controls and patients with neck pain but also between the two clinical phenotypes of Myofascial Pain Syndrome (MPS), namely groups that contain latent and active myofascial trigger points (MTrPs)¹⁰. Towards this, we propose to use the image texture features to construct a regularized logistic regression model in order to predict and discriminate between healthy controls and fibromyalgia affected muscle.

To summarize, our specific research questions are as follows:

- a. Can a regularized logistic regression model, built on texture variables extracted from B-mode ultrasound images of the upper trapezius discriminate between healthy, and FM subjects? Our hypothesis is that the model should effectively differentiate the two cohorts due to our previous work/success with other chronic pain disorders (MPS).
- b. How does regularization impact the overall performance of the trained model? Our hypothesis is that it should improve its generalizability.
- c. Does the holdout, test data validate the predicted performance of the logistic regression model? Our hypothesis is that it will be within 1 standard error of the prediction mean.

Methods & Design

Study Design:

The study conforms to the Consolidated Standards of Reporting Trials recommendations.

Ethical approval is approved by the University Health Network (UHN) Research Ethics Board.

This study is registered under the National Institutes of Health ClinicalTrials.gov. This proposed study is a diagnostic case-control study with one major independent binary outcome measure (FM present or Healthy), to create 2 patient cohort groups.

Participants:

Recruitment

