All images pre- and post-processing will be performed with MATLAB and the image processing toolbox¹¹. Images will be visually and statistically inspected for quality based on image intensity, contrast, and ability to discriminate muscle fibers. This is necessary to maintain a high standard of imaging data quality, and suspect no more than 15% of the data should be removed due to constraints. Next, since we are analyzing ROI's in the muscle we must extract only a certain number of frames from each video series. We will achieve this using an image filtering method that has been previously used by our group called the CW-SSIM¹² filtering method¹³. It will be used to objectively calculate and extract image frames from each video series in order to obtain the maximal number of images, while still maintaining uniqueness (minimal image overlap). After this procedure is finished we will extract a rectangular ROI estimation of the upper trapezius muscle excluding the upper and lower fascial borders. Lastly, the images will be labelled and organized for further processing.

Feature Extraction

Texture variables will then be extracted from the image ROI's using MATLAB and the image processing toolbox. The features to be extracted are as follows:

1. First order histogram parameters associated with image grayscale. These include mean, standard deviation, skewness, and kurtosis.

2. Gray level co-occurrence matrices (GLCM)¹⁴ will be calculated utilizing 4 directions (0,45,90,135 degrees). 76 variables are then created.
3. Lastly run-length parameters¹⁵ will be determined by gray level run-length matrices based upon the four given directions. Averaging the directions together gives seven features.

In total 88 feature variables will be extracted from each ROI, providing a feature descriptor dataset.

Elastic Net Regularized Logistic Regression

We will then construct and train an elastic net regularized logistic regression model on the dataset using the binary class labels constructed earlier¹⁶. This will be done using MATLAB and the Statistics and Machine Learning Toolbox¹⁷ and performed on a train/test split (80/20) of the original training data. The model will be regularized using the elastic net, which will improve the generalizability of the classification model on unseen data (avoid overfitting problems). The elastic net penalization method also provides a form of variable selection helping to minimize the effect of rank deficiency.

Model Validation

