The model will be validated using 10-fold nested cross validation on the training data due to the fact the model needs hyper-parameter tuning alongside the validation process. This requires a nested procedure where the hyper-parameter tuning is done in an inner loop and the validation of the model is in an outer loop. This will allow for an optimized, trained model that should generalize well to unseen data. This generalization will be tested using the final holdout set and will either confirm or deny whether the constructed model is a good classifier for this task.

Results

After the methodology is applied to all training data, performance metrics can be extracted from the results to demonstrate the model efficacy. Performance metrics like sensitivity, specificity, area under the curve (AUC) and accuracy will be extracted in order to characterize the model performance. These metrics will be averaged across the 10-folds (mean + stdev), and these values will be compared to the final metrics extracted from the holdout test set. If the test set values fall within 1 stdev, it will confirm the accuracy of the performance estimation during the training.

Primary Outcome

The primary outcome measures:

1. Binary classifier discriminates effectively (>70 % accuracy) between the healthy and muscle with FM.
2. Impact of regularization on the model performance.
3. Holdout test validation of the predicted performance.

Discussion

The overarching goal of our research utilizing image texture features is to eventually provide diagnostic aid to clinicians through the usage of clinically feasible, objective and reliable quantitative ultrasound techniques. While computer aided diagnosis research in ultrasound has been heavily explored in areas such as cancer and liver diseases¹⁸⁻²⁰, there has been little to no work in chronic pain¹³. This is the basis for this project proposal utilizing logistic regression modeling with elastic net regularization; the objective is to develop a statistical model with good predictive and diagnostic capabilities.

We are using logistic regression as our classification model due to its efficiency, computational resource requirement, interpretability, input feature scaling invariance, and ease of regularization²¹. The fact that logistic regression intrinsically calculates the predictive probability is a major strength of the model, as other classification techniques require further computationally intensive cross-validation to achieve this.

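### Primary outcome 1 calls the classifier effective on a point estimate above 70%, and the only spread planned, the SD over 10 folds, is not the standard error of that estimate (should fix)

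*Protocol*

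**What the plan says.** - **Protocol, Primary Outcome, item 1:** "Binary classifier discriminates effectively (>70 % accuracy) between the healthy and muscle with FM". No interval, lower bound, test or error rate is attached. The text does not say whether the accuracy is that of cross-validation or of the holdout, nor whether it is counted over images, sides or participants.
- **Protocol, Results:** "These metrics will be averaged across the 10-folds (mean + stdev), and these values will be compared to the final metrics extracted from the holdout test" (that is, the holdout data). The SD has one stated use: "If the test set values fall within 1 stdev, it will confirm the accuracy of the performance estimation during the training". It is not applied to the 70% threshold.
- **Protocol, Rationale for Utilization of Quantitative Ultrasound, research question c:** the same agreement rule is worded as "Our hypothesis is that it will be within 1 standard error of the prediction mean", so SD and standard error are used for one rule.
- **Protocol, Elastic Net Regularized Logistic Regression and Model Validation:** the work is "performed on a train/test split (80/20) of the original training data". On validation the text says "The model will be validated using 10-fold nested cross validation on the training data". The holdout result "will either confirm or deny whether the constructed model is a good classifier for this task".
- No sample size, power or error rate is stated anywhere. Trial Status gives recruitment as already complete.

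**The concern.** The headline conclusion is a yes/no statement about a threshold, yet it depends on which side of 70% a noisy estimate happens to fall. A reader told that the classifier is effective cannot tell an accuracy well above 70% from one at or slightly below it.

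The mean and SD over folds, printed beside the estimate, invite use as its precision. They are not that. The SD over folds describes how much a metric varies between small subsets of the training data. It is the standard error of neither the cross-validation mean nor the holdout accuracy. If folds are formed on images, the same participants recur across folds and the SD leaves out variation between participants. The protocol does not state the unit of the split.

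**Working it through.** The protocol gives no sample size or error rate, so there is no figure of its own to reproduce. Taken from it are the threshold (70%), the split (80/20) and the number of folds (10). Assumed are the number n of independent holdout participants, with one call each, and the true accuracy p.

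**1. How often the rule declares success.** The smallest passing count is r = floor(0.7n) + 1, and the probability is P(X ≥ r) with X binomial(n, p). For n = 20, r = 15, and at p = 0.70 the tail is 0.416.

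| n | r | true 60% | true 65% | true 70% |
|---|---|---|---|---|
| 12 | 9 | 22.5% | 34.7% | 49.3% |
| 20 | 15 | 12.6% | 24.5% | 41.6% |
| 30 | 22 | 9.4% | 22.5% | 43.2% |
| 40 | 29 | 7.1% | 20.5% | 44.1% |
| 100 | 71 | 1.5% | 12.4% | 46.2% |
| 200 | 141 | 0.1% | 5.8% | 47.3% |
| 400 | 281 | 0.0% | 1.5% | 48.1% |

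The whole-number threshold makes small sizes jump. At true 70% the rate is 38% for n = 10, 55% for n = 8 and 57% for n = 24. At true 65% it is 36% for n = 24.

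**2. The same rule read on the cross-validation mean.** This uses 80% of the total N, with folds treated as independent. At true 70% the rate is 44%, 46% and 47% for N = 50, 100 and 200. At true 65% it is 21%, 15% and 8%.

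**3. Fold SD against the standard errors.** Each fold holds 0.80/10 = 8% of the data. With participant-level folds treated as independent, at p = 0.70 and N = 100:

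- fold SD = sqrt(0.21/8) = 0.162
- SE of the cross-validation mean = sqrt(0.21/80) = 0.051
- SE of the holdout accuracy = sqrt(0.21/20) = 0.102

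The ratios do not depend on N or p: sqrt(0.80/0.08) = 3.16 and sqrt(0.20/0.08) = 1.58.

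**4. If images are counted.** Each participant gives two videos and several frames from each, so images are clustered. As an assumed example, take 20 participants with 10 images each and an intraclass correlation of 0.5. The design effect is 1 + 9 × 0.5 = 5.5, so 200 images carry the information of 200/5.5 ≈ 36. The SE is sqrt(0.21/36.4) = 0.076, not sqrt(0.21/200) = 0.032. By the normal approximation, a true 65% then passes about 26% of the time.

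**5. What a lower limit above 70% requires.** For an exact two-sided 95% interval at n = 20, P(X ≥ 18 | p = 0.70) = 3.5%, above 2.5%, so 18 fails. P(X ≥ 19) = 0.8%, so 19 passes. The Wilson lower limit for 18/20 is [0.9 + 0.0960 − 1.96 × sqrt(0.0045 + 0.0024)]/1.192 = 0.699, so 18 fails there too.

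**The case against.** **An unseen SAP may supply intervals.** Confidence intervals for accuracy and AUC are ordinary SAP content, and their absence from a protocol alone would be no finding. That stands as far as it goes. But the success rule and the fold summary are written into the protocol itself. An interval added elsewhere would sit beside a primary criterion that ignores it.

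**The fold SD does no harm to outcome 1.** A reader might infer that the fold SD is what lets weak classifiers through. The document does not support this. The SD is used only to judge agreement between holdout and cross-validation, and with participant-level folds it is too wide, which could not produce over-claiming. This part of the objection stands in full. What remains is that the SD cannot stand in for the missing standard error.

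**The size depends on N.** A reader might also infer that classifiers below 70% are often declared effective whatever the sample. That is not supported: at a true 65% the rate is 12% with 100 independent participants and 6% with 200. The protocol expects limited numbers of healthy controls (Limitations and Conclusions), which makes a small holdout plausible but does not establish one.

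**Any point threshold passes about half the time at its boundary.** True, and this is why a larger sample does not cure the 70% column. It matters here because the result is worded as effective or not.

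**This is early model development.** The work is described as a basis for further research, and no patient-care decision is tied to 70%. This limits the severity.

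**Conclusion.** The point holds. Outcome 1 declares effectiveness on a point estimate, and the one spread planned is not its standard error. At a true 70% the declaration is made about 40-50% of the time at most sizes (38-57% over all sizes tried). At a true 65% it is made about 21-35% of the time with 12, 20, 30 or 40 independent holdout participants, and much less often with 100 or more. All of this assumes one independent call per participant and a sample size that the protocol does not give. Counting clustered images as if independent would make the estimate look more precise than it is.

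This is a should-fix. A reader might take it as grounds for requiring a formal test against 70% before anything is reported. The document does not compel that: an honest interval, with wording that matches it, meets the concern.

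**What to change.** 1. Report accuracy, sensitivity, specificity and AUC with 95% confidence intervals that treat the participant as the unit. Use exact or Wilson intervals for proportions with one call per participant in a small holdout. Use a participant-level cluster bootstrap for AUC, for image-level metrics and, as an approximation, for pooled out-of-fold predictions. A percentile bootstrap is not enough for proportions in a small holdout. At n = 12 it passes 11/12, which a true 70% classifier reaches with probability 12 × 0.7^11 × 0.3 + 0.7^12 = 8.5%, against a nominal 2.5%.
2. Reword outcome 1. An observed accuracy above 70% is reported as an estimate with its interval. The text says that accuracy above 70% was demonstrated only if the lower limit of the two-sided 95% interval exceeds 70%.
3. State the dataset and unit to which the 70% applies.
4. Do not present the SD over folds as the precision of a metric. Reconcile SD and standard error between Results and research question c.

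**Cost:** protocol wording and a few lines of code, with no new data. The downside is real. At n = 20 the stronger statement needs 19 correct. With exact intervals, a classifier with true accuracy 80% would reach it about 7% of the time at n = 12 (12/12 needed) or n = 20, and 29% at n = 40 (34/40 needed). Since recruitment is complete, the conclusion may often be limited to the estimate and its interval.

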Regularization is a specific technique that is often used as a remedy to solve overfitting in classification models for machine learning²². In a general sense, regularization techniques are used to reduce a model's predictive error on unseen data by minimizing model variance with a given training set by smoothing the predictions. This is done by constraining (regularizing) the regression coefficients towards zero which discourage overly complex (flexible) models. What must be noted is that regularization does not improve the performance of the model on the data it was trained on. More intuitively, regularization acts as a penalty against complexity and steers the model away from memorizing (overfitting) the dataset. For this protocol we are utilizing elastic net regularization (a well-known technique) to improve the performance against the unseen data.

Until now, the literature shows that the diagnosis of FM remains challenging, in part due to its non-specific symptoms, which overlap with many other disorders such as myofascial pain syndrome. Even though patients who present symptoms such as chronic widespread pain, emotional distress, cognitive and sleep disturbances may be formally diagnosed with FM, it is possible that their primary disorder is not FM and has an entirely different pathophysiological mechanism. This protocol should demonstrate the effectiveness of texture analysis techniques when differentiating between FM patients and healthy individuals. Post-image acquisition texture analyses may provide some insight into the pathophysiology underlying FM.

Limitations and Conclusions

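### Primary outcome 2 asks what regularization does to performance, but the protocol specifies only the elastic net model and no comparator or contrast

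*Protocol*

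**What the plan says.** Only the protocol is at hand. Five places in it bear on this point.

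- **Research question b** (end of the rationale section) asks "How does regularization impact the overall performance of the trained model" and continues: "Our hypothesis is that it should improve its generalizability".
- **Primary Outcome**, item 2 of three, reads "Impact of regularization on the model performance". It gives no comparator, metric or threshold. Item 1, by contrast, carries an accuracy threshold of more than 70%.
- **Elastic Net Regularized Logistic Regression** describes the model: "We will then construct and train an elastic net regularized logistic regression model on the dataset". It adds "The model will be regularized using the elastic net, which will improve the generalizability of the classification model on unseen data", and says that the penalty also selects variables, "helping to minimize the effect of rank deficiency". The preceding Feature Extraction section gives 88 variables per region of interest.
- **Model Validation and Results** apply nested 10-fold cross-validation to that model, average sensitivity, specificity, AUC and accuracy over the folds, and compare the averages with the same model's holdout values.
- **Discussion** notes that "regularization does not improve the performance of the model on the data it was trained on" and commits again to the elastic net alone.

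**The concern.** A primary outcome should be obtainable from the analysis that the protocol describes. Here the outcome is comparative and the analysis has one arm. A team that followed the text exactly would finish with elastic net metrics and nothing to subtract from them.

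Two features make this more than an omitted detail. First, the Methods present the expected benefit as settled, although research question b treats it as a hypothesis to be tested. Second, the gap has no automatic solution. With many correlated texture features, ordinary maximum likelihood may give no unique or no finite answer, so somebody has to decide what stands for no regularization.

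The Trial Status section dates protocol version 1 to Sept. 10, 2019 and the end of recruitment to Sept. 6, 2019. Any comparator added now is therefore added after recruitment closed. It needs to be fixed before model results are seen.

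**Working it through.** **Step 1: match each primary outcome to a specified output.**

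| Primary outcome | What it needs | What the protocol specifies |
|---|---|---|
| 1. Accuracy above 70% | Accuracy of the elastic net | Fold averages and holdout accuracy: present |
| 2. Impact of regularization | Performance with the penalty minus performance without it, or with less | First term only; no second model, metric or contrast |
| 3. Holdout validation | Fold mean and SD against holdout, same model | Present in Results |

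The one comparison in Results has the same model on both sides. It shows how well cross-validation predicted holdout performance. It carries no information on what the penalty contributed.

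**Step 2: look for a comparator elsewhere.** The abstract speaks of regression models in the plural but names no unpenalised one. The inner tuning loop would normally try several penalty values, but the protocol gives no grid and no plan to report it, and tuning selects a model without estimating a contrast. The Discussion explains regularization in general terms. None of these supplies the missing term.

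**Step 3: ask whether the obvious comparator is well defined.** If the feature matrix is rank deficient, as the protocol expects, the unpenalised coefficients are not unique. If the two classes are linearly separable in the training data, the maximum-likelihood estimates are not finite.

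Cover's counting formula shows when separation is likely. For n independent rows in general position, p features plus an intercept (d = p + 1) and random labels:

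P(separable) = 2^(1−n) × Σ_{k=0}^{d−1} C(n−1, k)

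| Features p | n | P(separable) |
|---|---|---|
| 88 | up to 89 | 1 |
| 88 | 150 | 0.989 |
| 88 | 178 | 0.50 |
| 88 | 200 | 0.06 |
| 88 | 300 | 4 × 10⁻¹³ |
| 60 (assumed effective number) | 150 | 0.01 |
| 40 (assumed effective number) | 150 | 7 × 10⁻⁹ |

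The result runs from certainty to practically zero, depending on n and on the effective number of features. The protocol states neither. The formula also assumes independent rows, whereas the rows here are image regions clustered within participants (two videos each, several frames per video). The table shows that non-existence is possible. It is not a probability for this study.

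**Step 4: illustrate the dependence on the comparator.** All inputs here are assumed: 87 correlated features from 8 factors, one factor shifted by 1.2 SD, one row per participant, elastic net mixing weight 0.5, 60 replicates and 2,000 independent test subjects.

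| Training participants | Test AUC, lambda 1e-8 | Test AUC, lambda 0.1 | Difference |
|---|---|---|---|
| 40 | 0.70 | 0.73 | 0.03 |
| 80 | 0.67 | 0.76 | 0.09 |
| 160 | 0.66 | 0.78 | 0.12 |

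At 160 participants the gain was 0.12 against lambda 1e-8 but 0.03 against lambda 0.01. A repeat with similar assumed inputs and 25 replicates gave about 0.11 and 0.04. In this setting the choice of comparator changed the apparent benefit about three- to fourfold (0.11/0.04 ≈ 2.8; 0.12/0.03 = 4). The penalised arm used a fixed lambda, whereas the protocol tunes it, so these are not forecasts for the planned procedure.

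**The case against.** The best reply is that this belongs to a statistical analysis plan, which may exist but is not shown. The protocol gives the question, a direction, four metrics, outer folds and a holdout set. The phrase naturally implies a comparison with no regularization, and the exact penalty and interval method can be left for later. This stands in part. Interval method and software settings are proper analysis plan content, and the accurate wording is that no comparator is specified, not that none will ever be fitted. But the protocol is not silent on analysis. It sets out model, split, tuning, metrics and one comparison, and that set does not contain what a listed primary outcome contrasts.

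A second reply is that the statement of benefit in the Methods is ordinary optimistic rationale. Alone it would be minor. It matters because it pre-empts a primary question that the same analysis leaves untested.

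A third reply concerns the numbers, and it stands. The separation figures assume features in general position, which conflicts with the rank deficiency that the protocol expects, and the AUC gains rest on assumed inputs and a fixed penalty.

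Two stronger readings are tempting. A reader might infer that the unpenalised fit will certainly not exist in this study; without a sample size, that cannot be said. A reader might also infer that a later comparator could produce almost any benefit. The illustration shows only a several-fold range. The protocol's reliance on outer folds and holdout, with its remark about training data, also narrows the choice of data on which a comparison would reasonably be scored.

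**Conclusion.** The point holds on the text. Primary outcome 2 and research question b call for a contrast, and the protocol specifies only one side of it, so the analysis as written does not yield this outcome. This conclusion needs no numerical assumption.

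That the measured impact would depend on the choice of comparator follows from the protocol's own expectation of rank deficiency among its 88 features. The size of that dependence is unknown for this study, and every separation probability and AUC gain shown above is hypothetical.

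The change should be made, but the gap does not undermine the rest of the plan: outcomes 1 and 3 can be produced without it. An unseen analysis plan may already name a comparator. The protocol text would still need to agree with it.

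**What to change.** In the elastic net and validation sections, before any model results are examined:

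1. On the same features, the same outer folds and the same holdout, also fit a logistic model with one numeric near-zero penalty, fixed in advance and identical in every fold, for example lambda = 1e-6 on standardised features. A rule such as the smallest value on the tuning path is not enough, because no path is defined and a data-derived one can differ between folds.
2. Form folds and holdout by participant, so that all images from one person stay together for both models.
3. Define outcome 2 as the paired difference in out-of-fold AUC, tuned elastic net minus near-unpenalised model, with a 95% interval from a bootstrap over participants. Report the holdout difference as descriptive.
4. Reword the elastic net section so that better generalization is a hypothesis, in line with research question b.

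If the team does not want this comparison, it should remove item 2 from the primary outcomes and align research question b.

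The cost is a few lines of text and one extra model fit per fold. No new data are needed.
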